In the present study, we plan to investigate resistance mechanisms arising in ALK-positive NSCLC patients after progression while on a next generation ALK TKI using a plasma-based NGS platform. We will monitor the next treatment line received by those patients to assess the benefit derived from immediate access to subsequent lines of therapy based on the specific genomic profile identified by baseline plasma NGS. We plan to use a commercially available, CLIA certified, plasma NGS platform to offer noninvasive testing of the cfDNA to characterize the resistant tumor profile. Plasma NGS results will be returned to subjects and their provider to inform of the tumor genomics and possible sensitivities of any detected resistance mutations to available ALK TKIs.

Because it is now possible for patients to send plasma samples directly to central laboratories for NGS analysis, we will leverage a remote consent and participation approach to open enrollment to all nationwide patients with metastatic ALK-positive NSCLC. Our overarching hypothesis is that we can conduct a remote consent study using plasma NGS to characterize ALK resistance mechanisms arising at progression to a next-generation ALK TKIs, and predict the chance of response to different ALK TKIs according to the plasma NGS results.

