8 STUDY DESIGN

8.1 REMOTE CONSENT & PLASMA NGS

Our overarching hypothesis is that we can conduct a remote consent study using plasma NGS to characterize ALK resistance mechanisms arising in ALK positive NSCLC patients with progression while on a next generation ALK TKI, and that the chances of response to further treatment with a different ALK TKI can be predicted using those plasma NGS results.

This study will attempt to prospectively assess the resistance mechanisms detected by a plasma NGS assay in patients with advanced ALK positive NSCLC and systemic progression outside the brain using a web-based remote consent form process. Subjects will be sent blood collection kits with the necessary materials for local draws and those specimens will be sent directly by the subjects to the central laboratory (Resolution Bioscience) for plasma NGS. Plasma NGS results will be returned to the subject, their treating physician and study team, aiming to be returned within 2 weeks by Resolution Bioscience. This will allow prospective characterization of ALK resistant mutations arising in subjects after progression on different specific ALK TKIs. In addition, subsequent treatments and radiologic assessments received by the subjects will be prospectively monitored. A correlation between the ALK resistance mechanisms present at baseline, treatments received before and after plasma NGS assessments and outcomes will be analyzed.

We further propose here that plasma NGS could grant the ability to non-invasively detect specific ALK resistance mutations and, therefore, predict the sensitivity to different ALK TKIs and patients' outcomes. However, prospective CT-based response assessment is not feasible with a remote participation approach. We will instead use time to treatment discontinuation (TTD) as an alternate outcome. In collaboration with the US Food and Drug Administration (FDA), we found that TTD closely correlates with PFS outcomes in patients with genomic-driven lung cancer treated targeted therapies (manuscript in development), and is thus, well suited for studies of real-world evidence like ours. As such, we propose to evaluate the next treatment received by the subjects using TTD as the a time endpoint to assess treatment benefit. We also plan to analyze if plasma NGS results have any impact on the treatment decision process and if alterations in other relevant genes can impact subjects' outcomes.

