9 STUDY POPULATION

9.1 INCLUSION CRITERIA

- Men or women older than 18 years old at the time of consent or age of majority for residential state.
- Demonstration of having advanced ALK positive NSCLC.
- Systemic progression (not CNS only progression) within the past 30 days, having previously been treated with a next-generation ALK TKI.
- Patient must not have started a new line of therapy before signing the informed consent form.
- Willingness to provide a blood specimen prior to the initiation of a new line of treatment.
- Willingness to provide clinical and medical information to the study team as required.
- Ability to read, write and communicate in English.
- Ability to sign a web-based informed consent form.

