10.11 STUDY CALENDAR

Table 1: Times showed are estimations and can be adjusted with Principal Investigator approval if needed pending specific subject circumstances.

Visit Schedule	Registration, Enrollment and Visit 1 - Blood Collection		Follow-up Visits 2-5	Follow-up Visits 6-12	Visit 13/End of Study/Early Termination
	Screening ¹	Blood Collection	Up to 4 visits within 12 week window ⁴	Every 3 months from Enrollment ⁷ Visit 6 (+1 month) Visits 7-12 ±1 Month	Study end ³ 24 months -1 Month ⁷
Informed consent	x				
Registration	x				
Review inclusion & exclusion criteria	x				
Baseline blood collection kit		x			
Request medical records & imaging results	x			x ⁶	
Follow-up ⁴			x ⁴	x	x
Receive NGS report			x ⁵		
Send kit for optional blood draw			x ²	x ²	x ²

¹ Screening is permitted to extend as long as 30 days, if necessary.

² Optional blood specimens may be collected 1-3 weeks after initiation of a new therapy as well as when a subject's disease progresses on that therapy, prior to initiating subsequent line of therapy.

³ Subjects will be followed on study for a minimum of 8 months and for a maximum of 24 months if the study remains open or in follow-up, or until death.

⁴ Subjects weekly for 4 weeks, or as necessary per the subject's treatment plan. It is expected that at least two but no more than four study-specific Follow-Up visits will occur in the first 12 weeks.

(Visit 2 Week 1 ±3 days, Visit 3 Week 2 ±3 days, Visit 4 Week 3 ±3 days, Visit 5 Weeks 4-12)

⁵ The NGS Report is only received once during the 12 week follow-up, typically within 14 days.

⁶ Medical records & imaging results are only requested if attempts to reach the subject for follow-up have been unsuccessful, otherwise, data captured on disease progression and treatment changes are subject-reported.

⁷ 3 month visit windows include Visit 6 (3 months +1 month), Visits 7-12 (6,9,12,15,18,21 months ±1 month), Visit 13 (24 months -1 month)

Title: Study of Plasma Next Generation Sequencing for Remote Assessment, Characterization, Evaluation of Patients With ALK Drug Resistance (SPACEWALK)

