12 STATISTICAL CONSIDERATIONS

12.1 STUDY DESIGN & ENDPOINTS

A total of 300 subjects will be enrolled. Of those, we assume approximately 53% of the subjects (n=160) will have DNA shed and detectable ALK rearrangements, and will have progressed on either alectinib or ceritinib. Of the 160 subjects, we assume 80 subjects will have progressed on alectinib and 80 subjects will have progressed on ceritinib. Table 1 below shows the expected distribution of resistance mutations among these subjects.

Table 1: Expected distribution of resistance mutations

ALK mutation	Frequency after ceritinib	Frequency after alectinib
C1156Y	5%	0%
F1174X	15%	0%
I1171X	0%	10%
L1196M	0%	5%
G1202R	20%	30%
G1202del	5%	5%
D1203N	2%	0%
L1198F	5%	0%
C1156Y + L1198F	2%	2%
F1245C	0%	2%
No mutation	46%	46%

We will focus on two key mutational differences, F1174X and I1171X. With a type I error of 0.10, we have 99.8% power to detect the shown difference in acquiring the F1174X mutation, and 95.3% power to detect the shown difference in acquiring the I1171X mutation.

We will investigate response and time to treatment discontinuation (TTD) of those patients who have acquired an ALK mutation on their respective potential targeted therapy.

Table 2 below summarizes the maximum width of a 90% exact binomial confidence interval for response (CR+PR) to potential targeted therapy, per ALK mutation status.

Title: Study of Plasma Next Generation Sequencing for Remote Assessment, Characterization, Evaluation of Patients With ALK Drug Resistance (SPACEWALK)

Table 2: Max Width of 90% Exact Binomial Confidence Interval

ALK mutation	Total Sample Size	Number of Responses	Max Width of 90% CI
C1156Y	4	2	0.8043
F1174X	12	6	0.5093
I1171X	8	4	0.6143
L1196M	4	2	0.8043
G1202R	40	20	0.2779
G1202del	8	4	0.6143
D1203N	2	1	0.9491
L1198F	4	2	0.8043
C1156Y + L1198F	4	2	0.8043
F1245C	2	1	0.9491

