TTD is defined as the time from treatment start to treatment discontinuation for any reason, including disease progression, unacceptable toxicity, or death. For subjects who are alive without discontinuation, follow-up will be censored on the date of last adequate disease assessment. Table 3 below summarizes the intended TTD hazard ratios, median TTD improvement from 5 months, assuming exponential event time, power, and number of TTD events at full information with a Type I error of 0.10, for a total sample size of 10 or 20 subjects. TTD will be estimated using the Kaplan-Meier method and Cox proportional hazards models will be used to estimate hazard ratios. Comparisons of groups will be made using the log-rank test and Cox modeling.

Table 3: Time to Treatment Discontinuation

Total Sample Size	Number of events	Hazard Ratio	Median Survival	Median Survival After Therapy	1-Sided Type I Error Rate	Power
10	6	0.45	5 Months	12.5 Months	0.10	83%
20	14	0.50	5 Months	10 Months	0.10	89%

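### The therapy evaluated by TTD is not tied to the NGS report date, so a change prompted by the report can count as early failure of an interim drug

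*Combined protocol and SAP*

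**What the plan says.** The Abstract (Section 4) says the next line will be monitored to "assess the benefit derived from immediate access to subsequent lines of therapy based on the specific genomic profile identified by baseline plasma NGS". The therapy that TTD evaluates is then described in four ways:

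- Section 8.1: "we propose to evaluate the next treatment received by the subjects using TTD as the a time endpoint to assess treatment benefit".
- Section 8.2: the therapy begun after baseline plasma NGS, without saying whether that means the draw or the result.
- Section 10.9: the anticancer regimen that follows enrollment.
- Section 12.1: response and TTD in patients "who have acquired an ALK mutation on their respective potential targeted therapy". The term for that therapy is not defined.

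On timing, Section 9.1 has two conditions: "Patient must not have started a new line of therapy before signing the informed consent form" and "Willingness to provide a blood specimen prior to the initiation of a new line of treatment". Neither mentions the report. Section 8.1 sets a two-week target for returning results, and the Study Calendar (10.11) says: "The NGS Report is only received once during the 12 week follow-up, typically within 14 days". Under Section 10.3.1 the report goes to the subject and the treating physician and, for a detected ALK resistance mutation, gives expected sensitivity and resistance to alternate ALK inhibitors.

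On scoring, Section 12.1 states: "TTD is defined as the time from treatment start to treatment discontinuation for any reason". Section 10.8 counts either stopping the current treatment or starting a new systemic therapy as treatment failure. Censoring applies only to subjects alive without discontinuation. The clinical data listed in Section 10.5 do not include a reason for stopping.

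**The concern.** A subject may start a new drug after the baseline draw while the report is pending. If the report then leads to a different ALK inhibitor, the stated rules record a TTD event on the interim drug after roughly two weeks. No TTD rule covers the drug that follows. The study wants to observe whether results change treatment (Sections 7.2 and 8.1), yet that change is scored as failure.

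Disclosure of the biomarker can therefore trigger the endpoint that the biomarker is meant to predict. It does so mainly in subjects with a detected ALK resistance mutation, since their report gives expected drug sensitivities. Because four descriptions of the evaluated therapy coexist, the choice among them could also be made after the data are seen.

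**Working it through.** **Inputs**
- Table 3 (Section 12.1): reference median 5 months, exponential times, one-sided type I error 0.10. Row 1: N = 10, 6 events, median 12.5 months, power 83%. Row 2: N = 20, 14 events, median 10 months, power 89%.
- Sections 8.1, 9.1 and 10.11: a new line may start once consent and the draw are done; the report takes about 14 days.
- Not in the documents: q, the share who start before the report **and** change because of it, assumed 0-30%; s, time from start to switch, assumed 0.5 month and varied from 0.25 to 1.0.

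**Step 1. Reproduce Table 3.** Power = Φ(√d × |ln HR| − 1.282), with d events and HR the ratio of medians.
- Row 2: HR = 5/10 = 0.50; √14 × 0.693 − 1.282 = 1.312, so 90.5% (stated 89%).
- Row 1: HR = 5/12.5 = 0.40; √6 × 0.916 − 1.282 = 0.963, so 83.2% (stated 83%). The printed HR of 0.45 gives 75.0%. It disagrees with the row's own medians, which is a separate point to reconcile.
- Two-group formulas give only 25-51%. Table 3 is therefore a one-sample comparison with a fixed 5-month median.

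**Step 2. Median in a pooled analysis.** If a share q stops at s and the rest are exponential with median M, then after s the survival curve is (1 − q) × 2^(−t/M). The observed median is M × log2((1 − q)/0.5).

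| q | log2((1 − q)/0.5) | M = 10 | M = 12.5 |
|---|---|---|---|
| 0 | 1.000 | 10.0 | 12.5 |
| 10% | 0.848 | 8.5 | 10.6 |
| 20% | 0.678 | 6.8 | 8.5 |
| 30% | 0.485 | 4.9 | 6.1 |

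**Step 3. Power in a pooled analysis.** Let f be the Table 3 event fraction (6/10 or 14/20), λ = ln 2/M and λ0 = ln 2/5. Events O = N[(1 − q)f + q]. Exposure X = N[(1 − q)f/λ + q(1 − e^(−λs))/λ]. Apparent HR = O/(λ0X). Example for N = 10, q = 20%: O = 6.8, X = 87.5 months, λ0X = 12.1, HR = 0.56; √6.8 × 0.580 − 1.282 = 0.23, so 59%.

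| q | N = 10: HR, power | N = 20: HR, power |
|---|---|---|
| 0 | 0.40, 83% | 0.50, 90.5% |
| 10% | 0.47, 73% | 0.58, 80% |
| 20% | 0.56, 59% | 0.67, 61% |
| 30% | 0.67, 41% | 0.79, 37% |

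Taking s as 0.25 or 1.0 month moves power by at most about 3 points.

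**Step 4. Matched versus mismatched drugs.** Here the early stops fall on the mismatched interim drug. Suppose, for illustration, that mismatched therapy has the 5-month reference median and matched therapy 10 months. With 10, 20 or 30% of the mismatched group switching, its median reads 5 × 0.848 = 4.2, 5 × 0.678 = 3.4 or 5 × 0.485 = 2.4 months. The ratio of medians moves from 0.50 to 0.42, 0.34 or 0.24. The same rule now exaggerates the effect.

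**Step 5. Re-indexing versus omission.** If every switcher is re-indexed to the later drug, and that drug has the design TTD and follow-up, power returns to 83.2% and 90.5%. If switchers are simply left out, d becomes d(1 − q), and power at 10/20/30% is 80/77/73% (N = 10) and 88/85/81% (N = 20).

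**The case against.** The strongest reply is that Section 12.1 concerns the respective potential targeted therapy of mutation-positive patients. If that means the mutation-matched drug, an unmatched interim drug never enters the analysis. A reader might infer from Section 8.1 that the NGS-informed drug is not the one evaluated; Section 12.1 leaves that open, so only *may not be* is supported. The ambiguity stands, because the Section 12.1 term is undefined and the other sections say something else.

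Second, the hypothesis in Section 8.1 and the outcome objective in Section 7.2 are predictive. Baseline genotype is informative whether or not the physician had seen the report, so mixing informed and uninformed therapy is not in itself a bias. That is right. What remains is narrower: a discontinuation caused by the report is not evidence about the drug.

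Third, the share that matters is not everyone who starts early. Someone already on a drug reported as likely sensitive has no reason to change. If 10-30% start early and half of them switch (an assumption), q is 5-15% and the 10-month median reads 9.3 to 7.7 months. Kit shipment does not widen the window either, since it precedes the draw.

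Fourth, Section 8.1 plans to relate treatments before and after NGS to outcomes, and the Section 10.8 contacts document new treatment starts. This helps, but supplies neither an index regimen nor a reason for change. Section 10.10 foresees sequential lines for plasma sampling only.

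Finally, dropping report-prompted switches outright would depart from any-reason TTD and risk informative censoring.

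**Conclusion.** The concern holds as an undefined and inconsistent TTD index regimen, with a scoring rule that lets disclosure of the biomarker produce endpoint events. It bears only on subjects who start before the report and then change because of it. In a pooled one-sample analysis, an assumed share of 0-30% switching at about 0.5 month takes a 10-month median to between 10 and 4.9 months, and Table 3 power from about 83% to 41% (N = 10) and from about 90% to 37% (N = 20). At 0% there is no effect.

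Two stronger inferences are not supported. The bias is not always downward: in a matched-versus-mismatched comparison it inflates the contrast. Nor do the documents show that the planned effect would vanish; the fall to about the 5-month reference is the top of an assumed range in one form of analysis. The primary objective, which relates mutations to prior ALK TKIs, is untouched. This should be corrected, but it concerns a secondary objective.

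**What to change.** The change is to analysis and data capture only; nobody is asked to wait for the report or alter care.

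1. Reconcile Sections 8.1, 8.2, 10.9 and 12.1 on one TTD index regimen: the first systemic regimen started on or after the report date, or the regimen already running on that date if it is continued. Count time at risk from the report date for a regimen already running, using delayed entry. State how continued is judged.
2. At the existing follow-up contacts, record the report date, regimen start and stop dates, and reason for change, with an option for a change made because of the NGS result.
3. Keep any-reason TTD for the index regimen. Report a report-prompted switch off an interim regimen under the treatment-decision objective.
4. Add a sensitivity analysis under the current definition: first post-enrollment regimen, all discontinuations as events.
5. Describe pre-report and post-report starts without formally testing them as separate groups. Nine of the ten mutation groups in Table 2 have 2 to 12 subjects.

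The cost is endpoint wording and one CRF item. Delayed entry is awkward in groups this small. The reason for change will be largely subject-reported (Section 10.11, footnote 6), so some misclassification will remain; the sensitivity analysis shows how far the result depends on it.

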10.3.1 Baseline Plasma NGS

The forty (40) mLs of blood will be shipped directly to Resolution Bioscience's CLIA certified laboratory for analysis as per the standard processes. Laboratory staff will be blinded as to the subject's treatment history.

The results of plasma genotyping will be reported to the subject and the subject's primary treating physician. Resolution Bioscience will also release the results to the study team for inclusion in ALCMI's data repository.

The plasma NGS report will not include any specific treatment recommendations but will describe the presence of an ALK rearrangement, ALK resistance mutation, or other relevant mutations using language such as the following:

- If plasma NGS assay is negative for ALK rearrangement and negative for an ALK resistance mutation, this suggests levels of tumor DNA which are inadequate for detection of resistance mechanisms.
- If plasma NGS assay is positive for ALK rearrangement and negative for an ALK resistance mutation, this makes it difficult to predict sensitivity to alternate ALK inhibitors.
- If plasma NGS assay is positive for an ALK resistance mutation, the expected sensitivity and resistance of this ALK mutation to alternate ALK inhibitors will be provided. For example, the ALK resistance mutation G1202R confers resistance to crizotinib, ceritinib and alectinib while is sensitive to lorlatinib and there are controversial results regarding brigatinib activity. These will be expressed in the report using language such as: *Likely resistant to crizotinib, ceritinib and alectinib. Possible sensitivity to brigatinib. Likely sensitive to lorlatinib.* Appropriate scientific references will be provided.

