10.6 RADIOLOGY IMAGE COLLECTION & ANALYSIS

To characterize tumor response and study patient outcomes, CT images from subjects will be collected by the study staff and transferred to the Laboratory for Computational Imaging Analysis at Columbia University. This will be an exploratory analysis as we cannot control the quality and timing of these scans. This imaging analysis will complement the plasma response analysis.

Study staff will assist in obtaining copies of CT scans. For study staff to request copies of CT scan, study participants will be asked to complete a release form allowing their records to be obtained. The study staff will obtain the CT scans for all subjects and the release forms will be maintained in a locked filing cabinet. Up to 25 CT scans will be collected per subject, depending upon availability. PHI embedded in the images will be de-identified by the Laboratory for Computational Imaging Analysis at Columbia University prior to analysis. Using computer-aided-diagnosis software, each scan will be assessed. When serial imaging is available, change in nodule size will be characterized. Because each scan will already have undergone clinical review, no findings from the CT image analysis will be reported back to the subject.

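### TTD can be moved by the NGS report it is meant to test, and no planned analysis checks for report-driven stopping

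*Combined protocol and SAP*

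**What the plan says.** Half of the overarching hypothesis in section 8.1 is predictive: "the chances of response to further treatment with a different ALK TKI can be predicted using those plasma NGS results". The same section calls prospective CT-based response assessment infeasible under remote participation and substitutes TTD: "we propose to evaluate the next treatment received by the subjects using TTD as the a time endpoint to assess treatment benefit". It supports TTD by a correlation with PFS, from a manuscript still in preparation, in genomically driven lung cancer treated with targeted drugs.

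Section 12.1 gives the definition: "TTD is defined as the time from treatment start to treatment discontinuation for any reason". Section 10.8 defines treatment failure as the end of the current treatment or the start of a new systemic one, with no progression criterion.

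The report is not withheld from those who decide: "Plasma NGS results will be returned to the subject, their treating physician and study team, aiming to be returned within 2 weeks" (section 8.1). When an ALK resistance mutation is found, "the expected sensitivity and resistance of this ALK mutation to alternate ALK inhibitors will be provided" (section 10.3.1), with sample wording such as "Possible sensitivity to brigatinib. Likely sensitive to lorlatinib". The report makes no specific treatment recommendation. The only blinding stated is of laboratory staff, to treatment history.

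Other outcome information is planned. Section 12.1 summarises response (CR+PR) by ALK mutation, with 90% exact intervals in Table 2. Section 10.6 collects CT scans but adds: "This will be an exploratory analysis as we cannot control the quality and timing of these scans". In the section 10.11 calendar, footnote 6, unless contact with the subject fails, "data captured on disease progression and treatment changes are subject-reported".

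**The concern.** The predictor is the NGS result. The endpoint ends when the drug is stopped, and the people who stop it have read the predictor. A drug reported as likely sensitive may be continued longer after progression than it otherwise would be. One reported as likely resistant may be stopped sooner. Either would produce an association between NGS class and TTD that runs through the decision and not through the tumour, and in a comparison between classes the two effects add.

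At stake is how the secondary objective on outcomes by resistance mechanism and subsequent therapy is read, together with the predictive half of the hypothesis. A longer TTD in the favourable class could mean that NGS predicts sensitivity, or that the label changed when treatment stopped. The plan as written cannot separate the two. The investigators do intend to study whether NGS results affect treatment decisions (sections 7.2 and 8.1), but that analysis is not connected to TTD.

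**Working it through.** **Inputs from section 12.1 (Table 3 and text).** Reference median 5 months, exponential times, one-sided type I error 0.10. Row 1: 10 subjects, 6 events, HR 0.45, medians 5 and 12.5 months, power 83%. Row 2: 20 subjects, 14 events, HR 0.50, medians 5 and 10 months, power 89%.

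**Step 1: identify the test behind Table 3.** Take a one-sample exponential test against λ = ln 2 / 5 = 0.1386 per month. With d events and total time on treatment T, 2λT follows chi-square with 2d degrees of freedom under no effect, and the test rejects when 2λT exceeds the 0.90 quantile c. Power is P(chi-square(2d) > HR × c).

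- Row 2: c = 37.92; 0.50 × 37.92 = 18.96; power 89.9%. The log-HR approximation Φ(√14 × ln 2 − 1.2816) gives 90.5%. The plan states 89%.
- Row 1: c = 18.55. The printed HR 0.45 gives 75.7%. HR 0.40, which is 5/12.5, gives 82.9%, matching the stated 83%.
- Reading row 2 as a 1:1 two-group comparison gives only about 51%, so the table's figures are one-sample.

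**Step 2: add report-driven deferral with no true effect.** Suppose stopping times would be exponential with median 5 months without the report, and each stop is deferred by δ months. The values of δ are assumptions; the documents give none. If follow-up ends at the d-th event among N subjects, every observed time rises by δ, so T rises by Nδ and

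false-positive rate = P(chi-square(2d) > c − 2λNδ).

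- 14 of 20: 2λN = 5.545. For δ = 1, 2, 3 the threshold falls from 37.92 to 32.37, 26.83 and 21.28.
- 6 of 10: 2λN = 2.773. The threshold falls from 18.55 to 15.78, 13.00 and 10.23.

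**Step 3: defer only half the stops.** Death and toxicity are not discretionary, so each stop was deferred with probability 0.5 and the same test simulated.

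| Design | Stops deferred | δ = 0 | 1 month | 2 months | 3 months |
|---|---|---|---|---|---|
| 14 of 20 | all | 10% | 26% | 53% | 81% |
| 14 of 20 | half | 10% | 17% | 26% | 39% |
| 6 of 10 | all | 10% | 20% | 37% | 60% |
| 6 of 10 | half | 10% | 14% | 20% | 28% |

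**Step 4: vary the design.**

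- With follow-up as in section 12.2 (uniform 8 to 32 months, capped at 24), the one-sample rate starts near 8%. Deferring all stops gives 21%, 42% and 68% with 20 subjects and 15%, 26% and 41% with 10. Deferring half gives 14%, 21% and 31%, and 11%, 15% and 20%.
- Section 12.1 also plans log-rank comparisons. With 10 per group, the same follow-up and deferral of every stop in one group only, the rates are 19%, 28% and 38%, from 10% without deferral.

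**Step 5: compare with the target effect.** At 14 of 20, deferring every stop by 5 months gives a median estimated HR of 0.51, close to the planned 0.50, with no biological effect.

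**The case against.** **TTD is not the only benefit measure.** A reader might infer that nothing tumour-based is planned. That is wrong: section 12.1 plans CR+PR by mutation, and response does not depend on when the drug is stopped. This stands. However, section 8.1 calls prospective CT-based response assessment infeasible, the scan analysis is exploratory, and neither is tied to the TTD result.

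**The TTD–PFS correlation.** A reader might infer that it fails once physicians hold a predictive report. The documents do not show that either. The manuscript is not available, and whether its physicians had such information is not stated. It is fair to say only that the correlation is not shown to hold here.

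**The imaging laboratory.** A reader might infer that it reads scans knowing the NGS result. Nothing in section 10.6 says so: images are de-identified before analysis and assessed with computer-aided software. A blinding sentence would be a clarification, not the repair of a demonstrated fault.

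**The illustration may overstate the effect.** Some stops are not discretionary, the report recommends no treatment, and the plan's 5 months is a median TTD that may already include customary treatment after progression. Only deferral beyond custom counts. All of this stands, which is why the half-deferred rows are shown and no single figure is offered as an estimate.

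**A progression endpoint is imperfect too.** Progression is mostly subject-reported, contacts after week 12 are about every 3 months with a one-month window, and those who call progression hold the same report. This stands, and it rules out treating agreement between the two endpoints as proof.

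**Conclusion.** The concern holds as a limit on interpretation. The route from report to endpoint is in the documents, and the plan has no analysis that would reveal it. Under the stated assumptions, deferral of 1 to 3 months raises a nominal 10% error rate to between 14% and 39% in the two Table 3 designs if half the stops are affected, and to between 20% and 81% if all are. These figures rest on a 5-month exponential median, an uninformative report and assumed deferrals; the documents do not say whether or how much stopping would shift.

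The point does not show that a positive TTD result would be false. It does not touch the primary objective (section 7.1), which relates baseline mutations to prior ALK TKIs. It concerns a secondary objective and the predictive half of the hypothesis, and is worth correcting before outcome data are examined, because a reading rule added later would be post hoc.

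**What to change.** In section 12.1:

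1. Pre-specify, beside TTD, a sensitivity analysis of time from treatment start to progression or death, by NGS class. Use the progression information already captured, which is subject-reported, and take dates from medical records or collected scans where available.
2. Report the interval from progression to discontinuation, and the reason for stopping, by NGS class. This measures the suspected effect directly.
3. State that a TTD difference not seen in the progression analysis will not by itself be read as evidence that NGS predicts drug sensitivity.

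In section 10.6, state that the imaging laboratory reads without the NGS result, and use its reads as a supportive check.

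The cost is a few sentences of analysis plan, one further analysis, and some work to obtain progression dates and reasons for stopping from records or scans. The statistical price is that a positive TTD result alone supports a weaker conclusion. The change reduces the bias without removing it, for the reasons conceded above.
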